#### Outcomes

##### *Primary Outcome*

- Change from baseline in NRS pain scale at week 4 (Appendix B).

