Participant eligibility will be assessed according to inclusion and exclusion criteria in 2.0a. A member of the study team will describe the study and answer any of the participant's questions. The participant will then be consented and enrolled. The initial visit and all subsequent visits will include documentation of NRS pain scale (Appendix B), HS-PGA, Hurley Stage (Appendix C), clinical markers of inflammation, and lesion size (as specified in our standard approach to care. Photographs of the lesions will be obtained. The study personnel will administer a patient satisfaction survey and the PROMIS questionnaire, which will take 15 minutes to complete (Appendix D and Appendix F [or Appendix G if pediatric]). Chart review will record demographic information (age, gender, race, ethnicity, smoking status, and BMI) and complete blood count (CBC), basic metabolic profile (BMP), liver function tests (LFT), erythrocyte sedimentation rate (ESR), c-reactive protein (CRP), and interleukin-6 (IL-6). The lab work is a standard of care at the HSC independent of research objectives. The patient will receive an injection, not to exceed 2 mL per anatomic area, in up to 3 anatomic areas (total of 3mL). The patient will be counseled regarding potential side-effects of the treatment (Appendix H) and asked to monitor accordingly. No other changes to the patient's HS medication regimen will be made for the duration of the study.

- Phone Contact 1 (2-day post-treatment)

Since triamcinolone has a half-life of 18 to 36 hours, the initial patient follow-up will be a phone call at 2 days post-injection, lasting 15 minutes. Study personnel will administer a patient satisfaction survey and the PROMIS questionnaire (Appendix D, and Appendix F [or Appendix G if pediatric]). Additionally, patients will be asked if they experienced any side effects, including thinning/atrophy of skin, acneiform lesions, capillary dilation, and/or dyschromia.

- Phone Contact 2 (6 days post-injection)

This 15 minute phone call will be 6 days post-injection and will involve administering the patient satisfaction survey, the PROMIS questionnaire, and questions about side effects.

- Visit 2 (2 weeks post-injection)

- The initial screening visit examination will be repeated at week 2. Additionally, the patient will be asked to identify side effects. A patient

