#### Intralesional Triamcinolone Treatment Administration

While HS patients may have multiple sites of symptomatic disease, participants on this protocol will only receive treatment in up to three anatomic regions. These will generally be the most bothersome lesions to the patient. Networks of sinus tracks or the confluence of multiple nodules will be excluded as target treatment sites.

Treatment will only be administered by the blinded clinician on this study. Additionally, the clinical assessor and the patient will be blinded to the treatment group assigned. The patient will either receive normal saline, ILTAC-10, ILTAC-20, or ILTAC-40. Each lesion will be injected with up to 2 mL in up to 3 anatomic areas. The maximum treatment volume is 3 mL.

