### 3.0 STUDY POPULATION

- a) Study Population: The study population includes patients >13 years old with HS by a physician. All patients with HS-PGA greater than 2 will be included, regardless of comorbidities.
- b) Sample Size/Power Calculation: The primary outcome of our trial is a reduction in pain measures before and after treatment. We will have 4 groups: normal saline, ILTAC-10, ILTAC-20, and ILTAC-40. Of importance, these ILTAC doses are currently used for HS flares and are standard treatment for other dermatologic conditions, such as keloids. To estimate the sample size needed in each arm, we assumed that the pain score in our patients is normally distributed. The mean difference in pain score between normal saline and ILTAC-10 is estimated to be 1, with a standard deviation of 1, at baseline and also two days later, as is consistent with our clinical experience. We also assumed a range of correlations (0.1-0.9) that may be observed for a patient's pain score at the multiple follow-up points. When comparing normal saline and ILTAC-10, the most conservative of the treatment arms in terms of pain change, it is shown that at least 30 participants per arm are required to detect the anticipated effects (see Table 1 below for power calculations). Additionally, given that we expect to see a greater reduction in pain with ILTAC-20 and ILTAC-40, we will be more than sufficiently powered to detect the large pain reductions anticipated in the ILTAC-20 and ILTAC-40 groups. This conservative approach allows for the detection of a clinically meaningful change, as any substantial reduction in pain would result in clinical utilization of ILTAC.

**Table 1.** Tests for Two Groups of Pre-Post Scores. Numeric Results for Comparing Mean Change in a Repeated Measures Design. Null Hypothesis:  $\delta = 0$ . Alternative Hypothesis:  $\delta \neq 0$ . Results assuming a t-test.

| Target Power | Actual Power | N1 | N2 | N  | $\delta$ | $\sigma(T1)$ | $\sigma(T2)$ | $\rho$ | $\sigma(Diff)$ | Alpha |
|--------------|--------------|----|----|----|----------|--------------|--------------|--------|----------------|-------|
| 0.8          | 0.81021      | 30 | 30 | 60 | 1        | 1            | 1            | 0.1    | 1.342          | 0.05  |
| 0.8          | 0.81347      | 27 | 27 | 54 | 1        | 1            | 1            | 0.2    | 1.265          | 0.05  |

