| 0.8          | 0.8004       | 23 | 23 | 46 | 1        | 1            | 1            | 0.3    | 1.183          | 0.05  |
| 0.8          | 0.80321      | 20 | 20 | 40 | 1        | 1            | 1            | 0.4    | 1.095          | 0.05  |
| 0.8          | 0.80704      | 17 | 17 | 34 | 1        | 1            | 1            | 0.5    | 1              | 0.05  |
| 0.8          | 0.81254      | 14 | 14 | 28 | 1        | 1            | 1            | 0.6    | 0.894          | 0.05  |
| 0.8          | 0.82111      | 11 | 11 | 22 | 1        | 1            | 1            | 0.7    | 0.775          | 0.05  |
| 0.8          | 0.83633      | 8  | 8  | 16 | 1        | 1            | 1            | 0.8    | 0.632          | 0.05  |
| 0.8          | 0.87068      | 5  | 5  | 10 | 1        | 1            | 1            | 0.9    | 0.447          | 0.05  |

- Report Definitions
  - i. Target Power is the desired power value (or values) entered in the procedure. Power is the probability of rejecting a false null hypothesis. Actual power is the power obtained in this scenario. Because N1 and N2 are discrete, this value is often (slightly) larger than the target power. N1 and N2 are the number of items sampled from each population. N is the total sample size,  $N1 + N2$ .  $\delta$  is mean change of group 2 minus the mean change of group 1 assuming the alternative hypothesis.  $\sigma(T1)$  and  $\sigma(T2)$  are the standard deviations of measurements at time 1 and time 2, respectively.  $\rho$  is correlation between a pair of observations made on the same subject.  $\sigma(Diff)$  is the standard deviation of the paired differences, assumed equal for the two groups. Alpha is the probability of rejecting a true null hypothesis.
- Summary Statements
  - i. A 2-by-2 repeated measures design consists of two groups of subjects, each measured at two time points. In this case, the primary goal of the study is to compare the change across time in group 1 to the change across time in group 2. Sample sizes of 30 in group 1 and 30 in group 2 achieve 81% power to detect a difference in mean changes of 1.0 with a standard deviation of 1.0 at the first time point, a standard deviation of 1.0 at the second time point, and a correlation between measurement pairs of 0.100. The significance level (alpha) is 0.050 using a two-sided, two-sample t-test.
- c) Inclusion Criteria
  - Age > 13 years old.

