## 7.0 DATA ANALYSIS

- a) Statistical Methods  
We will analyze the data from the study using an intention to treat approach. Categorical variables, including presence of side effects, drainage, and physical function, will be analyzed with chi square tests. Continuous variables, such as NRS pain scale, markers of inflammation, and lesion size, will be analyzed by T-test. Sensitivity analyses or exploratory analyses may be performed to examine the effect difference for race or gender. In the unlikely case patients do not receive the treatment they will still be randomized for analysis using a per protocol approach. All statistical tests will be 2-sided, with  $p < 0.05$  considered significant.
- b) There will be no interim analysis or early stopping of the study.
- c) Confounding and effect modification will be addressed by randomization of the subjects and blinding of both the investigators and the participants.
- d) If subjects are lost to follow up, they will be analyzed in the group to which they were initially randomized.

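### Section 7.0 leaves baseline NRS out of the primary analysis; pre-specifying ANCOVA would add power and precision at no extra cost in patients

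*Combined protocol and SAP*

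**What the plan says.** The primary outcome (Section 2.0, Outcomes) is "Change from baseline in NRS pain scale at week 4". Section 7.0 a) gives the method: "Continuous variables, such as NRS pain scale, markers of inflammation, and lesion size, will be analyzed by T-test". Tests are two-sided at 0.05. Neither Section 7.0 nor any other section mentions ANCOVA, a regression model or a baseline covariate.

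The sample size in Section 3.0 b) matches a t-test on change. Table 1 compares mean change between two groups over correlations from 0.1 to 0.9. The summary statement takes 30 per group from the row with "a correlation between measurement pairs of 0.100", and adds: "The significance level (alpha) is 0.050 using a two-sided, two-sample t-test".

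Baseline pain is collected. Section 2.0 b), Visit 1, states: "The initial visit and all subsequent visits will include documentation of NRS pain scale". The study calendar in Section 5.0 f) also lists the NRS at enrollment.

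For physical function, Section 7.0 a) states: "Categorical variables, including presence of side effects, drainage, and physical function, will be analyzed with chi square tests". The secondary outcomes and Section 2.0 c), Aim 1, define it as change from baseline in a PROMIS score. Aim 1 treats a one-point change in either direction as clinically meaningful. No section ties the chi-square test to that threshold or says on which score scale a point is counted.

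**The concern.** A change score subtracts the baseline value with a coefficient fixed at 1. When baseline and week-4 pain are weakly correlated, the subtraction adds the noise of the baseline measurement without removing much between-patient variation. ANCOVA estimates the coefficient from the data. The plan sizes the trial at correlation 0.1, which is where a fixed coefficient of 1 costs most.

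At stake is the width of the interval for each ILTAC-saline difference, and the margin if the planning assumptions prove optimistic. SD 1 on a 0-10 scale rests on clinical experience and is stated for baseline and two days later, while the primary time point is week 4.

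For PROMIS, reducing a score to categories discards the size of the change, and a Pearson chi-square on three categories also ignores their order. Because the plan does not define the categories or the scale, both would have to be settled after it was written.

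**Working it through.** **Inputs** (Section 3.0 b), Table 1 and summary statement): n = 30 per arm, difference in mean change δ = 1, SD σ = 1 at both times, correlation ρ from 0.1 to 0.9, two-sided α = 0.05. All figures are for one comparison of an ILTAC arm with saline and assume 30 evaluable patients per arm.

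**1. Reproduce the plan's figure.** SD of change = σ√(2(1−ρ)). At ρ = 0.1 this is √1.8 = 1.342, as printed. Noncentrality = 1 / (1.342 × √(2/30)) = 2.887. With 58 df the noncentral t gives power 0.8102, which agrees with the printed 0.81021. The other eight rows of Table 1 also reproduce.

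**2. ANCOVA at the same n.** Residual SD = σ√(1−ρ²), which at ρ = 0.1 is √0.99 = 0.995. One df goes to the covariate, leaving 57. Chance baseline imbalance multiplies the variance of the difference by 1 + F/58 with F ~ F(1,58), on average 1 + 1/56 = 1.018, and power is averaged over F. With equal SDs the residual variance ratio, change score to ANCOVA, is 2(1−ρ)/(1−ρ²) = 2/(1+ρ). That is 1.8/0.99 = 1.82 at ρ = 0.1 and 1/0.75 = 1.33 at ρ = 0.5.

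| ρ | SD change | SD ANCOVA | Power, change | Power, ANCOVA | Gain (points) |
|---|---|---|---|---|---|
| 0.1 | 1.342 | 0.995 | 81.0% | 96.7% | 15.6 |
| 0.3 | 1.183 | 0.954 | 89.6% | 97.7% | 8.1 |
| 0.5 | 1.000 | 0.866 | 96.8% | 99.2% | 2.4 |
| 0.7 | 0.775 | 0.714 | 99.84% | 99.95% | 0.1 |

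Gains are taken from unrounded values. Simulation with an estimated slope (60,000 trials per cell) agrees: 81.1% vs 96.7% at ρ = 0.1 and 96.7% vs 99.2% at 0.5.

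**3. One model with all four arms** (pooled change score 116 df, ANCOVA 115 df): 81.7% vs 97.0% at ρ = 0.1; 90.1% vs 98.0% at 0.3; 97.0% vs 99.3% at 0.5.

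**4. The gain in other units.** To match two-arm ANCOVA at 30 per arm, the change-score test needs 53 per arm at ρ = 0.1, 45 at 0.3 and 39 at 0.5. The 95% CI half-width in NRS points, change score vs ANCOVA, is 0.69 vs 0.52 at ρ = 0.1, 0.52 vs 0.45 at 0.5 and 0.40 vs 0.37 at 0.7.

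**5. Larger SD at both times (assumption), change score vs two-arm ANCOVA:**

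| SD | ρ = 0.1 | ρ = 0.5 | ρ = 0.7 |
|---|---|---|---|
| 1.5 | 47% vs 72% | 72% vs 83% | 91% vs 94% |
| 2 | 29% vs 48% | 48% vs 59% | 69% vs 75% |

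**6. PROMIS.** Assumptions: normally distributed change with SD 1 to 10 points, saline mean change 0 to 0.5 SD, 30 per arm. A shift of 0.736 SD gives a t-test on change 80% power. For the same shift, a chi-square on improved/unchanged/declined at ±1 point has 42% to 59% power (200,000 simulated tables per cell). Its null rejection rate, checked at SD 1 and 5, is 4.8% to 4.9%, so the low power is not explained by a conservative test.

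**The case against.** The strongest reply is that nothing here is wrong. The planned test is valid, agrees with the outcome and the sample size, and reaches its stated power. Section 7.0 c) rightly relies on randomization to deal with confounding. All of this stands, but it answers bias and not precision.

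The 15.6-point gain is also the most favourable case. The correlation 0.1 is the worst case for a change score and is not offered as the expected value. This stands too, and the result should be read across the range of correlations.

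The ratio 2/(1+ρ) needs equal SDs at both times. In general the change score's excess variance is (SD at baseline − ρ × SD at week 4)², which can be zero. For illustration, take baseline SD 1 and ρ = 0.5. With week-4 SD 2 the powers are 59.4% (change) and 58.7% (ANCOVA); with week-4 SD 1.5 they are 82.1% and 82.8%. So the gain can vanish, but the loss is under one point. Table 1 itself assumes equal SDs.

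At ρ = 0.1 the gain comes from not subtracting baseline, more than from the covariate. If T-test meant raw week-4 scores, its power would be 96.8% at every ρ. Two-arm ANCOVA would then lose 0.1 point at ρ = 0.1 and gain 2.4 at 0.5 and 3.2 at 0.7, and the four-arm model would be level at ρ = 0.1. ANCOVA spares the plan from having to guess which unadjusted test will do better.

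On PROMIS, a chi-square on patients who do or do not improve by a point is a natural reading, though unwritten. Under the same assumptions it has about 51% to 62% power, still well below 80%.

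**Conclusion.** The point holds as a nearly free improvement that should be made. It does not correct an invalid analysis, and the stated 81% is met. Under Table 1's assumptions, ANCOVA raises power from 81.0% to 96.7% at ρ = 0.1 and from 96.8% to 99.2% at ρ = 0.5, with almost no gain from ρ = 0.7 upward. The practical value is greater if the SD exceeds 1: at SD 1.5 the gain is about 24 points at ρ = 0.1 (71.5 − 47.3) and 11 at ρ = 0.5 (82.8 − 71.9). Adjustment does not cure a wrong SD; it recovers part of the lost power.

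The figures rest on 30 evaluable patients per arm and on equal SDs at both times. They apply to one comparison at 0.05; multiplicity over three comparisons with saline is a separate matter.

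The PROMIS point is secondary. The missing link between test, threshold and score scale is plain from the text. The size of the power loss depends on assumptions that the plan does not supply.

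**What to change.** State in Section 7.0 a): *Week-4 NRS pain will be analysed by ANCOVA in one model with all four treatment arms as a factor and baseline NRS as covariate; adjusted mean differences versus saline will be reported with 95% confidence intervals.* Keep the sample size, and keep the change-score t-test as a sensitivity analysis so that Table 1 still corresponds to a reported test. The same sentence should say which pain rating is the primary NRS: Appendix D asks for pain at rest and pain when lesions are touched, and Appendix B does not choose between them.

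Lesion size at weeks 2 and 4 can be adjusted for its baseline in the same way once the plan names one measure per patient, such as a pre-specified index lesion or the sum over treated lesions. This is needed because "participants on this protocol will only receive treatment in up to three anatomic regions".

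Analyse PROMIS physical function as continuous with its baseline as covariate, and state the score scale. Appendix F has 10 items and Appendix G has 8, so keep adult and pediatric forms separate, or pool them only on a common score named in advance. The one-point categories can be reported as a supplement.

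The cost is about one sentence each for pain, the lesion measure and PROMIS, plus one degree of freedom per covariate. No new data or patients are needed. The text should be fixed before unblinding, so that the choice of covariate cannot be questioned later.

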### Study Objectives

#### *Aim 1*

- To compare the efficacy of ILTAC-10, ILTAC-20, and ILTAC-40 versus placebo for the treatment of acute HS flares.

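### Three doses are each tested against one saline arm at 0.05, with no multiplicity rule or deciding comparison: the chance of a false claim for at least one dose is 6.3%, not 2.5%

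*Combined protocol and SAP*

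**What the plan says.** - **Objective.** Section 2.0, Aim 1: "To compare the efficacy of ILTAC-10, ILTAC-20, and ILTAC-40 versus placebo for the treatment of acute HS flares". There are four arms, allocated equally, with one saline control.
- **Endpoint.** Section 2.0, Primary Outcome: "Change from baseline in NRS pain scale at week 4". Section 3.0 b) puts it differently: "The primary outcome of our trial is a reduction in pain measures before and after treatment". Neither place states the between-arm contrast.
- **Test.** Section 7.0 a): "Continuous variables, such as NRS pain scale, markers of inflammation, and lesion size, will be analyzed by T-test". The same paragraph adds "All statistical tests will be 2-sided" and sets p < 0.05 for every test.
- **Sizing.** Section 3.0 b) uses a two-sample t-test of saline against ILTAC-10 at undivided alpha 0.05. That pair is introduced as the cautious case, "When comparing normal saline and ILTAC-10, the most conservative of the treatment arms in terms of pain change", and is never called primary. The two higher doses are then said to be more than adequately powered, "given that we expect to see a greater reduction in pain with ILTAC-20 and ILTAC-40", so tests of those doses are also intended.
- **Hypothesis.** Section 2.0 expects ILTAC to be superior to saline without naming a dose, and separately expects a dose-dependent response.

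No section contains a multiplicity adjustment, a testing order, a global test or a rule for declaring success.

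**The concern.** A 0.05 threshold applied separately to three doses controls the error of each test. It does not control the error of the statement that at least one dose beats saline. Because the superiority hypothesis names no dose, a significant result at any one of the three could be reported as confirming it. The plan states no such success rule, so that step is an inference, but nothing in the plan prevents it.

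If the procedure is chosen after the results are known, the choice itself is open to challenge, because the reasonable procedures can give different answers on the same data. The stated 81% has a related limit: it is the power of one unadjusted comparison and says nothing about a family of three.

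**Working it through.** **Inputs from the plan.** 30 per arm; equal allocation; two-sided alpha 0.05; difference in mean change 1; SD 1 at each time; pre-post correlation ρ = 0.1 in the row used (Section 3.0 b, Table 1). The SD is given "with a standard deviation of 1, at baseline and also two days later", so every power figure below depends on day-2 inputs and is not a week-4 figure. No dropout is assumed.

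**Step 1: reproduce the plan's figure.** SD of change = √(2 − 2ρ) = √1.8 = 1.342. Noncentrality = 1 / (1.342 × √(2/30)) = 1 / 0.3464 = 2.887, with 58 degrees of freedom and critical value 2.002. Noncentral t power = 0.81021, which matches Table 1. The other eight rows also match.

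**Step 2: error if no dose works.** With equal arms and a common control, any two dose-versus-saline statistics correlate at 0.5. With c = 1.96, conditioning on the saline mean x:

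- favouring at least one dose: 1 − ∫ φ(x) Φ(c√2 + x)³ dx = 0.0627
- either direction: 1 − ∫ φ(x) [Φ(c√2 + x) − Φ(−c√2 + x)]³ dx = 0.1254

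Simulating 3,000,000 null trials of pairwise t-tests at 30 per arm gives 0.0627 and 0.1255. From 20 to 100 per arm, the rates stay at 0.0628–0.0629 and 0.1255–0.1256. Treating the tests as independent would overstate them: 1 − 0.975³ = 0.073 and 1 − 0.95³ = 0.143. The ratio to nominal is 0.0627 / 0.025 = 2.5.

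**Step 3: power under candidate procedures.** 30 per arm, SD 1, true difference 1 for every dose:

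| Procedure | ρ = 0.1 | ρ = 0.3 | ρ = 0.5 |
|---|---|---|---|
| One unadjusted test | 81% | 90% | 97% |
| Fixed sequence: 1st / 2nd / 3rd test | 81 / 70 / 63% | 90 / 83 / 77% | 97 / 94 / 92% |
| Holm, each dose | 74% | 86% | 96% |
| Dunnett-type (critical value 2.417), each dose | 68% | 80% | 92% |

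With all doses inert, the error favouring a dose is 2.5% for the fixed sequence, 2.5% for Dunnett-type and 2.2% for Holm.

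**Step 4: unequal effects (assumed; the plan gives only a difference of 1 for ILTAC-10).** ρ = 0.1; power for ILTAC-10 / 20 / 40:

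| Effects (10 / 20 / 40) | Order 10-20-40 | Order 40-20-10 | Holm |
|---|---|---|---|
| 1 / 1.25 / 1.5 | 81 / 78 / 78% | 78 / 94 / 99% | 79 / 92 / 98% |
| 0.5 / 1 / 1.5 | 29 / 28 / 28% | 28 / 81 / 99% | 28 / 73 / 97% |

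The order matters. If the first-tested dose is weak, it blocks the others.

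**Step 5: sensitivity to the SD (assumed).** With SD 1.5 at both times, the single unadjusted test has 47% power at ρ = 0.1 and 72% at ρ = 0.5. The error rates in Step 2 do not change.

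**The case against.** The strongest reply is that the inflation belongs to one reading of a plan that never writes out its contrasts. Three other readings remove it.

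1. The hypothesis could mean pooled ILTAC against saline, which is a single test. Aim 1 lists the doses one by one, and the sizing compares saline with a single dose, so this does not fit.
2. All three doses might have to succeed. The favourable error with all doses inert would then be only about 0.16%. No section states such a rule.
3. Each dose might be a separate question, reported at its own 5%. That position can be defended, but the plan would have to say so and give up any general claim that ILTAC works on the strength of one dose.

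These readings show that the decision rule is missing. None of them supplies it.

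Three points stand. The any-dose success rule is inferred. The documents do not give the study's present status, so the remedy assumes that it is still blind. An adjusted procedure also has a sample-size implication if the 80% target is to be kept; the figures are given with the fix. It is also fair that this is a single-centre dose comparison in which the choice among valid procedures belongs to the sponsor. Naming the contrasts and fixing some rule is not optional in the same way.

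**Conclusion.** The concern holds. As the plan reads, the week-4 claim that at least one dose beats saline carries a 6.3% chance of error in favour of treatment against a nominal 2.5%, or 12.5% against 5% in either direction. These figures assume three pairwise t-tests, equal arms, equal variances and no effect of any dose. They do not depend on the assumed difference, SD or correlation.

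The omission is certain from the text. That any one significant dose would count as success is an inference, though nothing in the plan rules it out. Because this concerns the primary efficacy claim and costs little to settle, it must be fixed before unblinding. Section 8.0 b) keeps assignments blinded until all data are recorded and validated. If that point has not been reached, the rule can still be set without knowledge of the results.

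**What to change.** Add one paragraph to Section 7.0 a) that names the three dose-versus-saline contrasts on week-4 NRS change and fixes one procedure. The options below are statistical testing orders, not dosing recommendations. Power is at ρ = 0.1 with the plan's inputs and equal effects unless stated.

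- **(a) Saline versus ILTAC-10 as the deciding test, or first in a fixed sequence at two-sided 0.05.** This is closest to the plan as sized and keeps alpha 0.05 and 81% for that contrast. In a sequence, the second and third doses have 70% and 63%. If ILTAC-10 fails, no formal claim is possible for the others; with assumed effects 0.5/1/1.5 they have 28% each.
- **(b) Fixed sequence ILTAC-40, ILTAC-20, ILTAC-10.** This follows the expected dose response but tests the sized contrast last. ILTAC-10 falls from 81% to 63% (78% with assumed effects 1/1.25/1.5). If ILTAC-40 fails, no formal claim is possible for the lower doses.
- **(c) Holm or a Dunnett-type test.** Any dose can succeed alone. Power per dose falls from 81% to 74% (Holm) or 68% (Dunnett-type). Restoring 80% would take about 34 per arm with Holm or 39 with Dunnett-type.

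If the sponsor wants the existing power statement to stand, (a) is the option that does so. If it wants any dose to be able to succeed on its own, (c) is the option, with power restated across the range of ρ.

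The paragraph should also label power as conditional on the day-2 inputs. It should place the secondary and dose-versus-dose comparisons outside the family-wise control and report them with confidence intervals. If a confirmatory dose-dependence claim is wanted, name one such contrast and include it in the family; as the last step of (a) or (b) it takes nothing from the earlier steps. Conduct does not change under any option, and the sample size changes only if (c) is chosen and the 80% target is kept.
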